2.2. Endpoints

Primary Endpoint:

- Time-to treatment discontinuation (TTD) is defined as the time from start of treatment to the date of discontinuation of these therapeutic methods.

Secondary Endpoints:

- Effectiveness: Objective Response Rate (ORR), duration of response (DOR) and TTP based on investigator's assessment; intracranial ORR (IC-ORR), IC-time to progression (IC-TTP), progression pattern ,1/2/3/4/5-year rwOS rate and OS;
- Safety: To explore the adverse events (AEs), the dose modification and the reason

for interruption or discontinuation of lorlatinib in first line for Chinese patients with ALK-positive locally advanced or metastatic NSCLC recorded in medical records;

[figure not shown]
- Adverse Events (AEs), as graded by NCI CTCAE (National cancer Institute Common Terminology Criteria for Adverse Events) v5.0; laboratory abnormalities (as graded by NCI CTCAE v5.0); vital signs (blood pressure, pulse rate) and body weight; electrocardiograms (ECGs); echocardiogram or MUGA (multigated acquisition) scan; ophthalmologic data;
- PRO as assessed by EORTC (European Organization for Research and Treatment of Cancer) QLC-C30;
- To describe the demographic, clinicopathological and baseline co-mutation characteristics of enrolled patients.

Exploratory Endpoints:

- Dynamic molecular response associated with lorlatinib treatment using ctDNA as measured by next-generation sequencing (NGS) if available in real world setting ;
- Biomarkers of sensitivity or resistance to lorlatinib in no-prior ALK-TKIs treatment tumor tissue and peripheral blood if available in real world setting;

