After lorlatinib treatment for 4 weeks, patients will receive an imaging assess. The patients who achieve PR or SD with oligometastasis (refer to target lesions with residual disease, a maximum of 3 organs, and no more than 5 lesions in total) should continue lorlatinib treatment and will receive imaging assess per 8-12 weeks. If target lesions indicate stable in 2 consecutive imaging, investigators will organize MDT and comprehensively evaluate patients' will to decide and choose local therapy. The local therapy includes surgery, ablation and, radiotherapy et al. After local therapy, patients should continue taking lorlatinib. While those who achieve CR or with multiple metastasis will continue lorlatinib treatment without any local therapy.

To dynamically monitor ctDNA changes in ALK + NSCLC patients during Lorlatinib treatment; to explore the correlation between ctDNA and Lorlatinib treatment efficacy .Patients need check the ctDNA-seq (10000x) in plamsa with NGS at baseline,4weeks after lorlatinib treatment and at disease progression.

Subjects will be on lorlatinib therapy until disease progression or unacceptable toxicity, new systemic anticancer therapy instituted, withdrawal of consent, death, or investigator decision dictated by protocol compliance, whichever occurs first.

Patients received continuous daily PO dosing of lorlatinib 100mg QD with/without locally therapy, from the date of first dosing (per the current protocol) or until one of the following criteria were met (whichever occurred first): disease progression; initiation of a new anti-cancer therapy; unacceptable toxicities; global deterioration of health-related symptoms; pregnancy; withdrawal of consent; loss to follow-up; death; investigator decision dictated by protocol non-compliance; or study termination. Patients who have progressive disease (PD) (per RECIST v1.1, by investigator review) and for whom the investigator believes it is in their best interest to continue lorlatinib treatment are allowed to continue lorlatinib therapy, at the discretion of the investigator, until any alternate or additional systemic anti-cancer therapy regimen was implemented.

At the time of progression and termination of study treatment, the patients could receive

any therapy at the judgment of the investigator. This study will take 1 years to enroll subjects, and each subject will be followed up for survival status and subsequent cancer therapies up to 60 months from the date of first dosing.

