7.2 Efficacy Assessments

7.2.1 Tumor Response Assessment

Objective tumor response will be measured using RECIST v1.1 (see Appendix 3) and assessed by the investigator (INV) in real world clinical practice .

Imaging tumor assessments at screening are to be performed within 28 days prior to commencing study treatment. All measurements should be recorded in metric notation using a ruler or calipers.

Investigators are encouraged to select greater than one lesion, representative and reproducible and to include the largest lesion, when identifying target lesions to be followed.

Post-baseline tumor assessments will be performed at the end of the first 8 weeks

then every cycle (within 7 days of the start of subsequent cycle including Day 1 of subsequent cycle), using the same method and technique used to characterize lesions identified at baseline. Imaging serves also as safety assessment to monitor/exclude pulmonary toxicity.

Subjects with no evidence of disease progression at the time of treatment discontinuation, should be followed up until disease progression, regardless of the start of any new cancer therapy. Repeat tumor assessments are suggested approximately every 4 weeks from the date of CT/MRI at the end of study treatment in the appropriate setting.

All subjects should be followed up for subsequent cancer therapies and survival status regardless of the reasons for discontinuation from study drug treatment. Telephone contact or other means to obtain timely regular follow-up is recommended. The information for subsequent therapies collected and recorded on the CRF should include enumeration of subsequent treatment, including drugs administered, date of initiation

and discontinuation of each drug. This may be conducted by telephone for unresponsive subjects. As per RECIST v1.1 guidelines, PR and CR do not need to be confirmed following initial response documentation. However, subjects with documented PR or CR should still be followed with regular assessments for the duration of the study to see if there is a change in status with time.

The same method and technique should be used to characterize each lesion identified and reported at Baseline, during the study treatment period, and during follow up.

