APPENDIX 3 RECIST Version 1.1

Adapted from E.A. Eisenhauer, et al: New response evaluation criteria in solid tumors: Revised RECIST guideline (version 1.1). European Journal of Cancer 45 (2009) 228–247.

CATEGORIZING LESIONS AT BASELINE

Measurable Lesions

Lesions that can be accurately measured in at least one dimension.

Lesions with longest diameter twice the slice thickness and at least 10 mm or greater when assessed by CT or MRI (slice thickness 5-8 mm)

Lesions with longest diameter at least 20 mm when assessed by Chest X-ray

Superficial lesions with longest diameter 10 mm or greater when assessed by caliper

Malignant lymph nodes with the short axis 15 mm or greater when assessed by CT.

NOTE: The shortest axis is used as the diameter for malignant lymph nodes, longest axis for all other measurable lesions.

Non-measurable disease

Non-measurable disease includes lesions too small to be considered measurable (including nodes with short axis between 10 and 14.9 mm) and truly non-measurable disease such as pleural or pericardial effusions, ascites, inflammatory breast disease, leptomeningeal disease, lymphangitic involvement of skin or lung, clinical lesions that cannot be accurately measured with calipers, abdominal masses identified by physical exam that are not measurable by reproducible imaging techniques.

Bone disease: Bone disease is non-measurable with the exception of soft tissue components that can be evaluated by CT or MRI and meet the definition of measurability at baseline.

Previous local treatment: A previously irradiated lesion (or lesion subjected to other local treatment) is non-measurable unless it has progressed since completion of treatment.

Normal sites

Cystic lesions: Simple cysts should not be considered as malignant lesions and should not be recorded either as target or non-target disease. Cystic lesions thought to represent cystic metastases can be measurable lesions, if they meet the specific definition above. If non-cystic lesions are also present, these are preferred as target lesions.

Normal nodes: Nodes with short axis <10 mm are considered normal and should not be recorded or followed either as measurable or non-measurable disease.

RECORDING TUMOR ASSESSMENTS

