Partial Response (PR): Greater than or equal to 30% decrease under baseline of the sum of diameters of all target measurable lesions. The short diameter is used in the sum for target nodes, while the longest diameter is used in the sum for all other target lesions. All target lesions must be assessed.

Stable Disease (SD): Does not qualify for CR, PR or Progression. All target lesions must be assessed. Stable can follow PR only in the rare case that the sum increases by less than 20% from the nadir, but enough that a previously documented 30% decrease no longer holds.

Progression Disease (PD): 20% increase in the sum of diameters of target measurable lesions above the smallest sum observed (over baseline if no decrease in the sum is observed during therapy), with a minimum absolute increase of 5 mm.

Indeterminate: Progression has not been documented, and

one or more target measurable lesions have not been assessed

or assessment methods used were inconsistent with those used at baseline

or one or more target lesions cannot be measured accurately (e.g., poorly visible unless due to being too small to measure)

or one or more target lesions were excised or irradiated and have not reappeared or increased.

Non-target disease

CR: Disappearance of all non-target lesions and normalization of tumor marker levels. All lymph nodes must be 'normal' in size (<10 mm short axis).

Non-CR/Non-PD: Persistence of any non-target lesions and/or tumor marker level above the normal limits.

PD: Unequivocal progression of pre-existing lesions. Generally the overall tumor burden must increase sufficiently to merit discontinuation of therapy. In the presence of SD or PR in target disease, progression due to unequivocal increase in non-target disease should be rare.

Indeterminate: Progression has not been determined and one or more non-target sites were not assessed or assessment methods were inconsistent with those used at baseline.

New Lesions

The appearance of any new unequivocal malignant lesion indicates PD. If a new lesion is equivocal, for example due to its small size, continued assessment will clarify the etiology. If repeat assessments confirm the lesion, then progression should be recorded on the date of the initial assessment. A lesion identified in an area not previously scanned will be considered a new lesion.

Subjective Progression

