Subjects requiring discontinuation of treatment without objective evidence of disease progression should not be reported as PD on tumor assessment CRFs. This should be indicated on the end of treatment CRF as discontinuation due to Global Deterioration of Health Status. Every effort should be made to document objective progression even after discontinuation of treatment.

Table 1. Objective Response Status at Each Evaluation

Target Lesions	Non-target Disease	New Lesions	Objective status
CR	CR	No	CR
CR	Non-CR/Non-PD	No	PR
CR	Indeterminate or Missing	No	PR
PR	Non-CR/Non-PD, Indeterminate, or Missing	No	PR
SD	Non-CR/Non-PD, Indeterminate, or Missing	No	Stable
Indeterminate or Missing	Non-PD	No	Indeterminate
PD	Any	Yes or No	PD
Any	PD	Yes or No	PD
Any	Any	Yes	PD

If the protocol allows enrollment of patients with only non-target disease, the following table will be used:

Table 2. Objective Response Status at each Evaluation for Patients with Non-Target Disease Only

Non-target Disease	New Lesions	Objective status
CR	No	CR
Non-CR/Non-PD	No	Non-CR/Non-PD
Indeterminate	No	Indeterminate
Unequivocal progression	Yes or No	PD
Any	Yes	PD

Best Overall Response

The best overall response (BOR) is the best response recorded from the start of treatment until disease progression. This is derived from the sequence of objective statuses. Objective statuses are not considered after objective progression is documented or after start of the first anticancer treatment post discontinuation of protocol treatment. BOR for each patient will be derived as one of the following categories.

Complete Response (CR): At least one objective status of CR documented before progression.

Partial Response (PR): At least one objective status of PR documented before progression.

Stable Disease (SD): At least one objective status of stable documented at least 8 weeks after start of treatment date and before progression but not qualifying as CR, PR.

Progressive Disease (PD): Objective status of progression within 12 weeks of start of treatment date, not qualifying as CR, PR or SD.

Indeterminate (IND): Progression not documented within 12 weeks after start of treatment date and no other response category applies.

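### Appendix 3 allows only PD or Indeterminate once a target lesion has been excised or irradiated as the study plans, so TTP, DOR and rwPFS in these patients depend on an unstated treatment of Indeterminate scans

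*Protocol*

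**What the plan says.** Section 3.1 describes the strategy. Patients in PR or SD with oligometastasis, defined there as residual disease in target lesions (at most 3 organs and 5 lesions), may be offered surgery, ablation or radiotherapy after two consecutive stable images. The protocol then says "After local therapy, patients should continue taking lorlatinib". Section 6.2.4 repeats the trigger.

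Section 7.2.1 makes the RECIST version in Appendix 3 the response criteria, applied by the investigator. In Appendix 3:

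- The definitions of CR, PR and SD for target disease each carry the condition "All target lesions must be assessed".
- Target disease is Indeterminate if progression has not been documented and "one or more target lesions were excised or irradiated and have not reappeared or increased".
- In Table 1 of the appendix, a target status of "Indeterminate or Missing" with non-target disease not progressing and no new lesion gives an overall status of Indeterminate.
- Progression remains recordable after local therapy, for example "The appearance of any new unequivocal malignant lesion indicates PD".

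The secondary endpoints in Section 2.2 include "duration of response (DOR) and TTP based on investigator's assessment", and Section 9.2.5 adds yearly rwPFS estimates. Section 9.2.1 defers censoring, naming PFS and OS but not TTP or DOR.

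**The concern.** The Indeterminate clause is a stock rule that suits local treatment given outside a trial's plan. Here excision or irradiation of a target lesion is the plan, so the strategy under study itself removes the patient's evaluable non-progression statuses from then on.

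Time-to-progression endpoints rely on scans without PD to keep patients at risk. If those scans are lost only for patients with a treated target lesion, and lost selectively because PD is still recorded, censoring becomes informative in the patients whom the study most wants to describe. Status is assigned at the site under Appendix 3, scan by scan, so the conflict enters the data before any analysis plan is applied.

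The reference for progression by target sum is also unclear. Appendix 3 measures PD from the smallest sum observed and does not say whether that sum still includes a lesion that has since been removed.

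**Working it through.** The protocol gives no figure to reproduce: its sample size is not derived from statistical assumptions, and this is a question of classification.

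**Step 1. Statuses available after excision or irradiation of a target lesion (Appendix 3, Table 1).**

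| Target disease | Non-target disease | New lesion | Overall |
|---|---|---|---|
| Indeterminate | CR, non-CR/non-PD or Indeterminate | No | Indeterminate |
| Indeterminate | PD | Yes or No | PD |
| Indeterminate | any | Yes | PD |
| PD (growth or reappearance) | any | Yes or No | PD |

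CR, PR and Stable cannot occur.

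**Step 2. The reference sum (assumed lesion sizes).** Two target lesions of 20 and 15 mm give a nadir of 35 mm. The 20 mm lesion is excised and the other grows to 22 mm. Against 35 mm the threshold is 1.2 × 35 = 42 mm, so this is not PD. Against the remaining 15 mm the increase is 7 mm, or 7/15 = 47%, which passes both the 20% and the 5 mm conditions, so it is PD.

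**Step 3. What the handling of Indeterminate scans can do to a 36-month estimate.** This is an illustration. Inputs from the protocol are the lorlatinib PFS rates of the cited phase 3 trial in Section 1 (78%, 68.2% and 63.5% at 12, 24 and 36 months) and 60 months of follow-up. Assumptions: the 24-36-month hazard continues to month 60; patients are progression-free at local therapy; local therapy falls at week 12 or week 28. Those weeks follow from scans at week 4 and then every 8-12 weeks: the second consecutive stable scan comes at 4 + 8 = 12 at the earliest, and a third scan at 12-week spacing at 4 + 12 + 12 = 28.

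S(60) = 0.635 × (0.635/0.682)² = 0.5505. With h = −ln(0.78)/12 = 0.0207 per month, S is 0.944 at week 12 (2.76 months) and 0.875 at week 28 (6.44 months).

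*(a) Indeterminate without PD counts as progression-free follow-up.* The estimate is the true conditional rate: 0.635/0.944 = 67% and 0.635/0.875 = 73%.

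*(b) Indeterminate is not evaluable; non-progressors are censored at local therapy and PD is kept at its date.* Only future progressors stay at risk, so the estimate is [S(36) − S(60)] / [1 − S(60)], with S conditional on being progression-free at local therapy:
- week 12: (0.672 − 0.583)/(1 − 0.583) = about 22%
- week 28: (0.726 − 0.629)/(1 − 0.629) = 26%

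Large-sample simulation gave the same values, with the median falling from not reached to about 16 and 20 months.

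*(c) PD after a run of non-evaluable scans is also censored at local therapy.* In the limiting case no events remain and the curve stays at 100%.

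**Step 4. Sensitivity under rule (b).** With one constant hazard, −ln(0.635)/36 = 0.0126 per month, and local therapy at month 4 or 7, the true rates are exp(−0.0126 × 32) = 67% and exp(−0.0126 × 29) = 69%. The formula gives (0.668 − 0.493)/(1 − 0.493) = 34% and (0.694 − 0.512)/(1 − 0.512) = 37%; simulation with 50 patients gave 35-38%. If only a share q of the patients is affected, the estimate is [S(36) − qS(60)] / [1 − qS(60)]; with q = 0.5 it is 56% and 59%.

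**Step 5. Whole population under rule (b).** With the Step 3 hazards, a true 63.5% becomes 59-60% if 20% of patients still progression-free at that time have a target lesion treated, and 47-49% if 60% do. Under rule (c) it stays near 63.5% if local therapy is unrelated to prognosis.

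**The case against.** The strongest reply is that the harm needs a censoring rule which the protocol does not contain. Indeterminate means by definition that progression has not been documented, and the one TTP-type definition given (intracranial, Section 9.2.4) runs to the first documented progression. Read that way, an Indeterminate patient has had no event and nothing removes that patient from risk. Censoring is commonly settled in an analysis plan, which may exist. This stands. A reader might infer that TTP and DOR in locally treated patients are necessarily distorted, or necessarily look worse; the documents do not support that, because rules (a) to (c) give no bias, downward bias and upward bias.

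Other limits also stand:

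- The clause names excision and irradiation. Ablation is not named, and treatment of non-target lesions only does not trigger it, so not every locally treated patient is affected.
- The sentence "A previously irradiated lesion (or lesion subjected to other local treatment) is non-measurable unless it has progressed since completion of treatment" may look like further support, but it belongs to the categorisation of lesions at baseline.
- Intracranial lesions in patients with brain metastases are assessed by RANO-BM (Section 3.1), so the argument does not carry over to IC-TTP.
- TTD, as defined in Sections 2.2 and 9.2.2, is not computed from RECIST status.
- A PR recorded before local therapy is kept in best overall response. Only a patient still in SD at that point loses the chance to be recorded as a responder.
- Section 9.2.5 names no TTP subgroup by local therapy, and the study is described as descriptive.

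The reply does not remove the conflict. The clause and Table 1 are stated rules, they contradict what the strategy needs, and the deferral in Section 9.2.1 names neither TTP nor DOR. An analysis plan could settle censoring, but the reference sum would still have to be defined where sites read scans.

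**Conclusion.** The point holds as a conflict between Appendix 3 and the study's own strategy. After planned excision or irradiation of a target lesion, only PD or Indeterminate can be recorded, and no exception is written.

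The effect on TTP, DOR and rwPFS is conditional. Under the assumed rule that Indeterminate scans are not evaluable, a true 36-month rate of 67-73% reads about 22-38% in patients who all had a target lesion treated. Other rules leave it unchanged or push it up to 100%. These figures illustrate the rate of being progression-free; they rest on the assumed hazards and timing, are not forecasts for this study, and DOR was not computed separately. That defensible rules can give such different answers for the same patients is the reason to settle the matter. It should be fixed, but it does not threaten the primary endpoint.

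**What to change.** Add one paragraph to Appendix 3, for endpoint derivation, covering target lesions excised, irradiated or ablated as protocol local therapy:

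1. A later scan with no new lesion, no non-target PD and no growth or reappearance of treated or remaining lesions is an adequate non-PD assessment for TTP, rwPFS and DOR.
2. Target-sum progression is judged against the nadir of the untreated target lesions.
3. If all target lesions were treated, progression is judged by regrowth or reappearance, non-target PD or new lesions. This case must be covered, because both the oligometastasis definition and Appendix 3 cap the count at 5 lesions.
4. The best-response and ORR window in Section 9.2.4 and Appendix 3 stays as it is.

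The cost is a paragraph and a matching entry on the tumor assessment form; treatment does not change. The small downside is a departure from the letter of Appendix 3: status after local therapy is non-PD, which is not a RECIST response and should be reported as such.

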APPENDIX 4 PRO Instrument

- EORTC QLQ-C30 (version 3)

EORTC QLQ-C30 (version 3)

We are interested in some things about you and your health. Please answer all of the questions yourself by circling the number that best applies to you. There are no "right" or "wrong" answers. The information that you provide will remain strictly confidential.

Please fill in your initials:

Your birthdate (Day, Month, Year):

Today's date (Day, Month, Year):

	Not at All	A Little	Quite a Bit	Very Much
1. Do you have any trouble doing strenuous like carrying a heavy shopping bag or a suitcase?	1	2	3	4
2. Do you have any trouble taking a long walk?	1	2	3	4
3. Do you have any trouble taking a short walk	1	2	3	4
4. Do you need to stay in bed or a chair during	1	2	3	4
5. Do you need help with eating, dressing, yourself or using the toilet?	1	2	3	4
During the past week:	Not at All	A Little	Quite a Bit	Very Much
6. Were you limited in doing either your work or	1	2	3	4
7. Were you limited in pursuing your hobbies or	1	2	3	4
8. Were you short of breath?	1	2	3	4
9. Have you had pain?	1	2	3	4
10. Did you need to rest?	1	2	3	4
11. Have you had trouble sleeping?	1	2	3	4
12. Have you felt weak?	1	2	3	4
13. Have you lacked appetite?	1	2	3	4
14. Have you felt nauseated?	1	2	3	4

15. Have you vomited?	1	2	3	4
16. Have you been constipated?	1	2	3	4
17. Have you had diarrhea?	1	2	3	4
18. Were you tired?	1	2	3	4
19. Did pain interfere with your daily activities?	1	2	3	4
20. Have you had difficulty in concentrating on things, like reading a newspaper or watching television?	1	2	3	4
21. Did you feel tense?	1	2	3	4
22. Did you worry?	1	2	3	4
23. Did you feel irritable?	1	2	3	4
24. Did you feel depressed?	1	2	3	4
25. Have you had difficulty remembering things?	1	2	3	4
26. Has your physical condition or medical treatment interfered with your family life?	1	2	3	4
27. Has your physical condition or medical treatment interfered with your social activities?	1	2	3	4
28. Has your physical condition or medical treatment caused you financial difficulties?	1	2	3	4

For the following questions please circle the number between 1 and 7 that best applies to you

29. How would you rate your overall health during the past week?

1 2 3 4 5 6 7

Very poor

Excellent

30. How would you rate your overall quality of life during the past week?

1 2 3 4 5 6 7

Very poor

Excellent

© Copyright 1995 EORTC Quality of Life Group. All rights reserved. Version 3.0
